4.3 Hospital Stay

Hospital stay is measured by hospital length of stay (LOS) from admission to discharge.

The hypotheses to be tested are:

$$H_0: \text{Median}_A = \text{Median}_S \text{ versus } H_A: \text{Median}_A \neq \text{Median}_S$$

Where Median_A and Median_S are the median hospital length of stay for the Ampion and placebo groups. Assuming there is no censoring, this will be tested using the Wilcoxon rank sum test via PROC NPAR1WAY. If censoring occurs, e.g., death, then the log rank test will be used based on PROC LIFETEST.

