### Length of Stay (LOS)

Due to the COVID-19 health emergency, the Centers for Medicare and Medicaid is temporarily allowing long-term care facilities not normally used as a resident's room to accommodate beds and residents for care in emergencies/situations needed to help with surge capacity. Therefore, hospitalization refers to hospital and/or inpatient care during the COVID-19 health emergency. Inpatient care may include hospitals treating COVID-19 patients; dedicated COVID-19 treatment facilities with 24/7 care; and/or dedicated research facilities with 24/7 care.

Dates of hospitalization and ICU admission as well as discharge dates will be recorded at hospital discharge, Days 28 and 60, as applicable. Hospital discharge will be clinically indicated as the time when patients no longer require 'in hospital' and/or 'in patient' care in the hospital and/or inpatient care unit. A patient will be considered 'moved out of the ICU' when they are transitioned and/or stepped down from the ICU. Patients will be defined as "stepdown" by exclusion (i.e., that they no longer meet any criteria for full intensive care). These patients may still require frequent monitoring and/or nursing care and may also have some minimal organ support requirement but no longer remain in the ICU (Prin, 2014).

The hospital LOS and ICU LOS will be calculated as follows:

- ICU admission: defined (in days) as the first study day when ICU status is changed to "yes" minus baseline date + 1
- Hospital LOS: is defined (in days) as the date of hospital discharge minus date of hospital admission + 1
- ICU LOS: defined (in days) as the date moved out of ICU minus first study date when ICU admission changed to "yes" + 1

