2.3 Study Design

This is a Phase II randomized, double-blinded, placebo-controlled study to evaluate the safety and efficacy of inhaled Ampion in adults with respiratory distress due to COVID-19.

Interested COVID-19 patients will sign the appropriate informed consent document(s) prior to completion of any procedures. The investigator will review inclusion and exclusion criteria prior to any invasive procedures. If the patient is eligible after this review, the site will perform the necessary, if any, study procedures to confirm eligibility.

Participants will be randomized 1:1 to active or placebo using a random allocation sequence stratified by disease severity (severe, critical). The general sequence of events during the treatment and assessment period:

- Complete baseline procedures and sample collection.
- Participants are randomized to Ampion or placebo.
- Participants receive study intervention (active or placebo) inhaled via nebulization for 5 days.
- Complete safety monitoring, study procedures, and sample collection through Day 60.

All subjects will receive the standard of care (SOC) for COVID-19, which may include:

- Oxygen administration to maintain oxygen saturation of 90% or greater, including the use of supplemental oxygen, NIV, and mechanical ventilation circuits.
- Nursing physical that may include review of neurological; pulmonary; cardiac; gastrointestinal; and urinary assessment at least daily during treatment.
- Vital monitoring (heart rate, blood pressure, temperature, respiratory rate, SpO2) at least daily during treatment.
- Telemetry monitoring to evaluate heart rhythm and rate.
- Diet as tolerated to satisfy nutritional needs.
- Treatments for COVID-19 symptoms including antibiotics, cough suppressants/expectorants, anti-coagulants, fever reducers/pain killers, anti-nausea drugs, and/or bronchodilators.
- Treatments for COVID-19 as approved by the FDA including expanded access, emergency, or compassionate use (i.e., remdesivir, dexamethasone, convalescent plasma).
- Medications will be recorded as concomitant medication, tabulated, and compared among groups.

The clinical effects, safety, and tolerability of treatment will be evaluated from baseline through Day 60. Evaluations at screening and during the 5-day treatment occur in person. Evaluations after the 5- day treatment to the end of the study (days 7 to 60) will typically occur via telephone contact unless the patient is in an inpatient setting.

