2.4 Sample Size

The trial is designed for approximately 200 patients across two treatment arms (active or control), with a 100 subjects per arm, randomized 1:1 using a random allocation sequence stratified by COVID-19 disease severity (severe or critical).

The number of participants is selected based on the effects observed for the primary endpoint, all-cause mortality. A study in the New England Journal of Medicine with over 4,000 patients receiving the standard of care (SOC) for COVID-19 found a 26% mortality rate at Day 28 (NEJM 384;8, February 25, 2021). There was a similar observation in the Ampion Phase I study (AP-014) for patients with respiratory distress due to COVID-19 with a mortality for the SOC control arm of 21% by Day 28. In the AP-014 study, a lower mortality rate (8%) was observed for subjects receiving inhaled Ampion. Assuming the same proportions of deaths (8% for Ampion and 26% for control) by Day 28, the number of subjects (n=200) achieves at least 80% power.

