Assess the effect of Ampion compared to placebo on intensive care	
Percentage of participants who require Intensive Care Unit (ICU) admission by Day 28.ICU-free days through Day 28.ICU LOS from ICU admission to discharge.

Assess the effect of Ampion compared to placebo on all-cause mortality	
 Percentage of participants with a successful outcome (life) or unsuccessful outcome (death) by Day 28.
--	--

The efficacy endpoints will be evaluated to estimate the treatment effect and use descriptive statistics including mean, standard deviation, percentages, minimum/maximum, and 95% confidence intervals. All endpoints will be tabulated and presented by treatment arm, cohort (moderate and severe), and timepoint. Where appropriate, data will be tabulated and presented cumulatively across cohorts and/or timepoints.

All binary outcomes are single incident percentages and thus the differences between the treatment groups will be tested using Fisher's exact test. The length of stay endpoints are also single incident endpoints the differences between the treatment groups will be tested using two sample t-test. All the other change from baseline variables are repeated assessments and will be analyzed utilizing a repeated measures analysis of variance.

Exploratory endpoints assess the effect of inhaled Ampion treatment compared to placebo on the clinical outcomes for participants with respiratory distress due to COVID-19 as follows:

Objective	Endpoint
Exploratory	
Assess the effect of Ampion compared to placebo on cytokine profile	
 Modulation of cytokine levels from baseline to Day 5.

The efficacy endpoints will be evaluated to estimate the treatment effect and use descriptive statistics including mean, standard deviation, percentages, minimum/maximum, and 95% confidence intervals. All endpoints will be tabulated and presented by treatment arm, cohort (moderate and severe), and timepoint. Where appropriate, data will be tabulated and presented cumulatively across cohorts and/or timepoints.

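### Hospital length of stay: one test censors deaths and another has no rule for them, so deaths are under-penalised and the t-test can favour the arm with more deaths

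*SAP*

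**What the plan says.** Three places govern the hospital LOS comparison, and they do not agree.

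- **SAP 4.3 (Hospital Stay)** compares medians. "Assuming there is no censoring, this will be tested using the Wilcoxon rank sum test via PROC NPAR1WAY". It then adds: "If censoring occurs, e.g., death, then the log rank test will be used based on PROC LIFETEST". Death is the only example of censoring given. SAP 4.6 repeats both rules for ICU LOS, where the test is labelled exploratory and outside the hierarchy.
- **The opening part of SAP 4, and Protocol 9.4.2**, give a different test: "The length of stay endpoints are also single incident endpoints the differences between the treatment groups will be tested using two sample t-test". Neither says what value a patient who dies in hospital receives.
- **Protocol 5.2** gives the definition: hospital LOS "is defined (in days) as the date of hospital discharge minus date of hospital admission + 1". A patient who dies in hospital has no discharge date, so no LOS follows from this definition.

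The only rule that gives death a worst value (Protocol 9.5, SAP 8.1) applies to missing ordinal scores in a sensitivity analysis. It does not reach LOS. In the hierarchy, hospital LOS comes after adverse events and the two NEWS2 comparisons, and ahead of all-cause mortality, which is last.

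**The concern.** Death ends any chance of discharge. Censoring at death treats the patient as someone who would have gone home at the same rate as those still in hospital. The t-test must either stop the stay at death or leave the patient out. None of these options counts death as a bad outcome for LOS.

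This matters when deaths are common and unequal, which is what the sample size section assumes. A treatment that keeps very sick patients alive adds long stays to its own arm, while the comparator's deaths drop out or count as finished stays. The LOS step could then fail, or point towards the arm with more deaths. Because mortality is tested later, failing at LOS would also remove the formal mortality test for a drug that had lowered mortality.

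**Working it through.** **Inputs from the documents.** 100 per arm, 1:1. SAP 2.4: "Assuming the same proportions of deaths (8% for Ampion and 26% for control) by Day 28". Final alpha 0.047, two-sided (SAP 7.1). Follow-up to Day 60 (SAP 5.7). The only LOS figures are Phase I averages of 7 and 11 days, with no spread (Protocol 2.3). No power is stated for LOS.

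**The plan's own figure.** SAP 2.4 says "the number of subjects (n=200) achieves at least 80% power", for mortality. Power = Φ{(|p1−p2|√n − z√(2p̄(1−p̄))) / √(p1(1−p1)+p2(1−p2))}, with p1 = 0.08, p2 = 0.26, p̄ = 0.17, n = 100:

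- alpha 0.05: (0.18×10 − 1.960×0.5312)/0.5158 = 1.471, power 92.9%
- alpha 0.047: (1.8 − 1.986×0.5312)/0.5158 = 1.444, power 92.6%

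The statement holds as a lower bound.

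**Will the death rule be used?** Expected deaths are 100×0.08 + 100×0.26 = 34. Yes, almost certainly.

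**Assumptions not in the documents.** Stays are lognormal: ordinary survivors median 8 days (log-SD 0.6); time to death median 9 days (log-SD 0.5). Under the plan's rates, 26 − 8 = 18 per 100 Ampion patients are rescued. Their stay is varied: ordinary, or median 14 or 20 days (log-SD 0.4).

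**Direction of the t-test, by arithmetic.** A lognormal mean is median × exp(SD²/2): ordinary 8×exp(0.18) = 9.58; death 9×exp(0.125) = 10.20; rescued 14×exp(0.08) = 15.17 or 20×exp(0.08) = 21.67.

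- Deaths dropped, 20-day case: Ampion (74×9.58 + 18×21.67)/92 = 11.95; control 9.58. Ampion looks 2.4 days worse.
- Death ends the stay, 20-day case: Ampion (74×9.58 + 18×21.67 + 8×10.20)/100 = 11.81; control (74×9.58 + 26×10.20)/100 = 9.74. Ampion looks 2.1 days worse.
- Death ends the stay, ordinary case: Ampion (92×9.58 + 8×10.20)/100 = 9.63; control 9.74. No material difference, despite 18 fewer deaths.

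**Simulation** (700 to 2,000 trials per scenario, two-sided 0.047; chance alone gives about 2.35% in each direction):

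| Deaths, control vs Ampion | Rescued stay | t-test favours high-death arm | Censored log-rank favours high-death arm | Censored log-rank favours Ampion | Deaths kept as not discharged: favours Ampion |
|---|---|---|---|---|---|
| 26% vs 8% | ordinary | about 2% | 0% | about a third | 83–87% |
| 26% vs 8% | 14 days | 17–21% | 0.7% | 8.4% | – |
| 26% vs 8% | 20 days | about 50% | 6–7% | about 1% | 35% (Day 28), 55% (Day 60) |
| 10% vs 5% (illustrative) | 20 days | 8–9% | about 3% | – | – |

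In the 20-day case at 26% vs 8%, the t-test result is about the same whether death ends the stay or is dropped. Keeping deaths as not discharged favours placebo in 0% at either horizon. Simulation error near 3% with 1,000 trials is about ±2×√(0.03×0.97/1000) = ±1.1 points.

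**A second model** gives both arms the same underlying discharge times (median 7 days, log-SD 0.7), with 26% vs 8% deaths and 3,000 trials. If deaths are unrelated to discharge, the censored log-rank favours the high-death arm in 2.1% and the low-death arm in 2.9%: no penalty at all. Across five death patterns the t-test favours the high-death arm in 17% to 96%. Keeping deaths as not discharged to Day 60 favours it in 0.0% and the low-death arm in 40% to 72%. With 17% deaths in each arm, every method rejects in 4.5% to 5.2%.

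**The case against.** A death-censored log-rank test is a recognised comparison of the discharge rate among patients still in hospital. It does not ignore death entirely, because a patient who will die stays in the risk set, undischarged, until then. With ordinary rescued stays it favours the low-death arm in about a third of trials. A reader might infer that this test routinely rewards the arm with more deaths. The documents do not support that. Larger reversals (13.0% and 58.6% in the second model) arise only when deaths come early and fall mainly or wholly on patients who would have had long stays, and nothing in the plan says so.

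A reader might also infer that the plan counts death as a short stay. It does not say how a death enters the t-test.

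The 20-day stay is an assumption, and the t-test reversal shrinks quickly without it. The mortality inputs may also be too high: Protocol 3.2.1 itself reports that progression to ventilation or death has fallen since earlier in the pandemic. Death is scored worst on the primary ordinal scale and tested separately, and the hierarchy may stop before LOS is reached. Days in hospital before randomisation are balanced by randomisation and mainly add noise.

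All of this limits the size. It does not remove the conflict between the tests, the missing rule for deaths, or the place of LOS ahead of mortality.

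**Conclusion.** The point holds in a bounded form. The documents prescribe conflicting tests for hospital LOS, and none treats death as a failure to be discharged. At 8% vs 26% mortality the censored log-rank under-penalises death or does not penalise it. It is often merely insensitive, favouring the high-death arm in about 0–7% of trials in the main scenarios. The t-test is the more serious problem: about 2%, 17–21% and about 50% for ordinary, 14-day and 20-day rescued stays. With 5% vs 10% deaths and 20-day stays the figures fall to about 8–9% (t-test) and 3% (log-rank).

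These percentages rest on assumed stay and death-time distributions, so the range should be read, not any single value. What needs no such assumption is that the texts conflict, that LOS is undefined for in-hospital deaths, and that failing at LOS blocks the formal mortality test. For ICU LOS the consequence is smaller, because that test is exploratory.

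**What to change.** Specify one hospital LOS test in both documents:

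- **Endpoint and test:** time from randomisation to live discharge. Patients who die are kept as not discharged to a fixed, stated horizon, and the arms are compared by log-rank or cumulative incidence.
- **Horizon:** choose it deliberately. In the 20-day scenario Day 28 gives about 35% power and Day 60 about 55%. Day 60 is already the end of follow-up.
- **Remove** the two-sample t-test for LOS from Protocol 9.4.2 and SAP 4, and the instruction in SAP 4.3 to censor at death.
- **Report** raw LOS from admission descriptively.
- **Apply** the same death rule to ICU LOS, still exploratory.

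The cost is a protocol correction as well as new SAP text, because the t-test and the LOS definition are protocol wording and Protocol 10.3 requires a written amendment. It should be done before unblinding. No new data are needed: hospital dates and mortality are already recorded (Protocol 5.2).

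The SAP should name the downside. The new test mixes mortality with speed of discharge: with ordinary rescued stays, where survivors' stays are alike in both arms, it still favours Ampion in 83–87% of trials. A significant result must not be described as faster recovery alone.

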4.4 Oxygen Use

Oxygen use is measured by the change in oxygen use, blood oxygen saturation, and oxygen flow rate from baseline through Day 5.

The hypotheses to be tested are:

$$H_0: \mu_A = \mu_S \text{ versus } H_A: \mu_A \neq \mu_S$$

Where μ_A and μ_S represent the mean percent change from baseline in the various measures at day 5 for Ampion and Placebo after randomization. The difference between Ampion and Placebo with respect to the percent change from baseline at day 5 will be tested utilizing a two-sample t-test via PROC TTEST, or the Wilcoxon rank sum test via PROC NPAR1WAY depending on whether a transformation to normality can be found or not.

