## 2.3 Previous Human Experience

Human serum albumin (HSA, 5%) is a human blood product approved by FDA for intravenous (IV) infusion to treat hypovolemia and other serious conditions, including ARDS (Polito 2013). Albumin and large molecules are removed to manufacture Ampion, the low molecular weight (< 5 kDa) ultrafiltrate of 5% HSA.

Ampion has been administered via inhalation to humans with severe COVID-19 in a Phase I clinical trial utilizing inhaled Ampion in treating respiratory distress in patients as a result of COVID-19 (AP-014). The results from this study to date (n=27 subjects) indicate inhaled Ampion may be safe and well-tolerated with no differences in the incidence, frequency, and severity of adverse events for patients treated with Ampion compared to control. Preliminary results from the AP-014 Phase I trial of inhaled Ampion indicate:

- **Ampion demonstrated an improvement in all-cause mortality in COVID-19 patients compared to standard of care (SOC).** A lower all-cause mortality rate of 8% is observed for the Ampion treatment group, compared to 21% in standard of care alone.
- **Patients who received Ampion required less hospitalization time.** The average hospital length of stay was 7 days for the Ampion group compared to 11 days for standard of care patients.
- **Patients who received Ampion required less oxygen** than standard of care alone, and 86% of Ampion patients were stable or had improvement compared to 75% of SOC patients.
- **More patients who received Ampion were stable or had improvement** on a scale of clinical improvement compared to standard of care alone. By day 5, 86% of patients who received Ampion were stable or had improvement compared to 75% of standard of care patients. This trend in improvement with Ampion treatment is noted as early as day 2 and continues to day 5.
- **Adverse events were the same between Ampion and standard of care,** and no drug-related serious adverse events have been reported.

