#### 5.1.3 Treatment Period (Day 1 to Day 5)

The following procedures will be performed during the Treatment Period (Day 1 to Day 5) while subject is hospitalized for the index hospitalization:

- Begin inhalation treatment of study intervention (active or placebo) daily within 6 hours of randomization.
- Concomitant medications/therapies

- Vital signs: heart rate, systolic and diastolic BP, body temperature, respiratory rate
- SpO2 and supplementation oxygen mode/flow rate
- ECG monitoring (telemetry) or 12-lead ECG: record aberrant changes in waves/ intervals.
- Hematology, biochemistry tests – these tests are performed at baseline and every other day through treatment and through hospital.
- Cytokine and chemokine assays – these tests are performed at baseline and at Day 5.
- Ordinal scale and NEWS2 assessments
- Aes

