### Cytokine and Chemokine Assays

Cytokine and chemokine assay lab test results will be collected and recorded before the first treatment, after the last treatment, and at hospital discharge. A cytokine panel is tested to include, but not limited to: Tumor Necrosis Factor alpha (TNF $\alpha$ ), interferon gamma (IFN $\gamma$ ), Interleukin 1 beta (IL-1 $\beta$ ), interleukins (IL-6, IL-8, IL-10, IL-12). Data is reported for research purposes, and the sample is destroyed after data is collected.

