### 7.1 Dosing and Administration of Study Medication

Ampion treatment will be provided as a solution in glass vials ready for human use and treatment administration. Appropriately trained site personnel will administer the study treatment.

Participants will receive a daily dose (32 mL/day) of study intervention (active or placebo) through nebulized inhalation delivered in four equally divided doses of 8 mL, every 6 hours (q\_6), for 5 days. Treatment should commence within 6 hours of randomization. Treatment should terminate at the end of the 5-day treatment period, or when a patient is discharged, whichever comes first.

As outlined in [Section 2.1](#), Ampion or placebo will be delivered in nebulized form to patients using the Aeroneb® Solo Nebulizer System (manufacturer Aerogen Limited, Galway, Ireland), which consists of the Aerogen® Pro-X Controller and the Aerogen® Solo adaptor. Study intervention (active or placebo) aerosolized using the Aeroneb® Solo Nebulizer will be delivered *via* an appropriate aerosol delivery assembly for inhaled drug administration as clinically indicated, *e.g.*, using the hand-held Aerogen Ultra, NIV, and/or a mechanically ventilated circuit. The aerosol delivery assembly used to deliver aerosolized Ampion to each patient will be determined at the treating physician's discretion based on the severity of respiratory illness and clinical needs of the patient at enrolment and continuing throughout the study. Appropriate settings for aerosol delivery assembly respiratory parameters (*e.g.*, supplemental O2 content, flow rate, inspiratory/expiratory pressure, etc.) will be determined for each patient by the treating physician on an ongoing basis as clinically indicated.

Participants will be monitored for any respiratory and/or cardiac distress via vital sign monitoring including respiratory rate, heart rate, and blood pressure daily throughout the study product treatment period.

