4.2 Clinical Health

Clinical health is measured by the change in NEWS2 from baseline to Day 5, and baseline to hospital discharge.

The hypotheses to be tested are:

$$H_0: \mu_A = \mu_S \text{ versus } H_A: \mu_A \neq \mu_S$$

Where μ_A and μ_S represent the mean change from baseline in the NEWS2 score assessment through day 5 for Ampion and Placebo after randomization. The difference between Ampion and Placebo with respect to the change from baseline at day 5, or discharge if earlier, will be tested utilizing a Wilcoxon rank-sum test via PROC NPAR1WAY. To assess any potential time trends an exploratory repeated measures analysis of variance will be performed with terms for treatment, time and the interaction between the two. This will be done utilizing PROC GLM with the REPEATED option.

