4.8 Cytokine Profile

The exploratory endpoint, cytokine profile, is measured as the modulation of cytokine levels from baseline to Day 5.

The hypotheses to be tested are:

$H_0: \mu_A = \mu_S$ versus $H_A: \mu_A \neq \mu_S$

Where μ_A and μ_S represent the mean percent change from baseline in the cytokine levels at day 5 for Ampion and Placebo after randomization. The difference between Ampion and Placebo with respect to the percent change from baseline at day 5 will be tested utilizing a two-sample t-test via PROC TTEST. To assess any potential time trends, an exploratory repeated measures analysis of variance will be performed with terms for treatment, time, and the interaction of the two. This will be done utilizing PROC GLM with the REPEATED option. Also, the rates of the various adverse events and serious adverse events will be presented in tables, but otherwise not analyzed statistically.

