9.6 Efficacy Analyses

The efficacy of treatment on the clinical course and outcome of COVID-19 will be evaluated by comparing to placebo. Summaries will be performed by severity (severe or critical), individually, and combined.

Unless otherwise specified, continuous variables will be summarized with the number of non-missing observations, mean, standard deviation, median, minimum, maximum and 95% confidence intervals displayed. Data transformation or use of rank-based tests may be used if endpoints depart substantially from a normal distribution. Categorical data will be summarized as counts, percentages and 95% confidence intervals.

Differences between treatments will be presented using mean differences and 95% confidence intervals. Endpoints will be compared between treatment groups (Ampion or control).

Except where otherwise specified, missing data will not be estimated or carried forward in any of the descriptive analyses. No multiple comparison adjustment will be done for the secondary efficacy analyses. If the data clearly violate the distribution assumptions of the model, then transformations may be applied, or rank-based methods used.

The efficacy analyses of the endpoints are detailed in Section 3 and Section 4 above.

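### The Day 5 oxygen test has no rule for patients discharged (or dead) before Day 5, so it analyses a subset selected by outcome and would dilute a real effect on recovery

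*SAP*

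**What the plan says.** **Test.** The endpoint covers oxygen use, SpO2 and oxygen flow from baseline through Day 5. SAP 4.4 says the arms' difference "with respect to the percent change from baseline at day 5 will be tested utilizing a two-sample t-test via PROC TTEST", with the Wilcoxon rank-sum test as the alternative if no normalising transformation is found. It says nothing about patients who leave earlier.

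**Same situation, NEWS2.** SAP 4.2 says the difference "with respect to the change from baseline at day 5, or discharge if earlier, will be tested utilizing a Wilcoxon rank-sum test".

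**Collection.** Protocol 5.1.3 lists SpO2 and oxygen mode/flow among procedures done on Days 1 to 5 "while subject is hospitalized for the index hospitalization". The Schedule of Assessments continues SpO2 daily until discharge and does not mark it at Day 28 or 60. Protocol 5.1.5 (follow-up) lists neither SpO2 nor flow.

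**Early discharge.** Protocol 7.1 ends treatment after five days "or when a patient is discharged, whichever comes first".

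**Missing data and population.** SAP 9.6 states that "missing data will not be estimated or carried forward in any of the descriptive analyses". The only efficacy imputation, in SAP 8.1, is a sensitivity analysis for the ordinal scale. SAP 6.1.2 places all efficacy analyses in all randomized patients.

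**A second method for the same endpoint.** The general text of SAP section 4 and Protocol 9.4.2 assign repeated measures analysis of variance to the remaining change-from-baseline variables.

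**The concern.** A patient discharged on Day 2, 3 or 4 has no Day 5 oxygen value and no substitute for it. The test as written compares only patients still in hospital on Day 5, and being in hospital on Day 5 is itself an outcome. A patient who dies before Day 5 drops out in the same way.

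If Ampion speeds recovery, more Ampion than placebo patients leave early, and those removed are the ones who did best. The remaining groups look more alike than the randomized groups. At stake is a biased, underpowered comparison on a secondary endpoint, in an analysis labelled intent-to-treat.

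The exploratory cytokine test has a weaker form of the same mismatch. SAP 4.8 uses "the mean percent change from baseline in the cytokine levels at day 5 for Ampion and Placebo after randomization", while Protocol 5.2 takes samples "before the first treatment, after the last treatment, and at hospital discharge".

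**Working it through.** **1. The plan's own power figure.** The only one is for Day 28 mortality: 26% v 8%, 100 per arm, at least 80%. With pooled rate 0.17, the null SE is √(2×0.17×0.83/100) = 0.0531. The alternative SE is √(0.26×0.74/100 + 0.08×0.92/100) = 0.0516. Power = Φ[(0.18 − 1.96×0.0531)/0.0516] = 92.9% at α = 0.05, and 92.6% at the final 0.047. The statement holds as a lower bound but says nothing about oxygen.

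**2. Share gone before Day 5.** No such rate is given. Protocol 2.3 reports, for Phase I, "The average hospital length of stay was 7 days for the Ampion group compared to 11 days for standard of care patients". *Assumption:* stays follow a gamma distribution with these means and shape k, so the share is F(t; k, mean/k), with t = 4 or 4.5 days. For k = 1 and t = 4.5 this is 1 − exp(−4.5/7) = 47.4% and 1 − exp(−4.5/11) = 33.6%.

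| Shape | t = 4: Ampion v control | t = 4.5: Ampion v control |
|---|---|---|
| 1 | 43.5% v 30.5% | 47.4% v 33.6% |
| 2 | 31.7% v 16.5% | 36.8% v 19.8% |
| 3 | 24.7% v 9.8% | 30.4% v 12.6% |
| 4 | 19.8% v 6.0% | 25.8% v 8.4% |

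The range is about 20–47% v 6–34%. Stay runs from admission, not from study Day 1. If each patient had already spent two days in hospital at Day 1, the shares would be 43–50% v 17–34%.

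**3. Effect on the estimate and power.** *Assumptions:* Day 5 improvement Y has SD 1 and a true difference of 0.4 SD. A patient leaves early if Z = ρY + √(1−ρ²)·e exceeds a cut c that gives control share q. There are 100 per arm and two-sided α = 0.047.

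- Everyone scored: 0.4/√(2/100) − 1.986 = 0.842, so power is 80%.
- Leavers dropped: each arm's mean becomes μ − ρφ(a)/Φ(a), with a = c − ρμ.
- Example, q = 20% and ρ = 0.6: c = 0.842. Ampion: 0.4 − 0.6×0.3329/0.7263 = 0.125. Control: −0.6×0.2800/0.80 = −0.210. Difference 0.335 SD.

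Simulation (3,000 trials per setting, t-test):

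| Control share q, ρ | Lost, Ampion v control | Estimate | Power |
|---|---|---|---|
| 10%, 0.3 | 12% v 10% | 0.39 SD | 73% |
| 20%, 0.6 | 27% v 20% | 0.34 SD | 61% |
| 30%, 0.9 | 44% v 30% | 0.22 SD | 36% |

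Also dropping early deaths (3% on control) in the middle row gives 0.32 SD and 58%.

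**4. No true effect.** Loss is equal between arms, bias is about zero, and rejection is 4.3–5.7% across settings, which is simulation noise around 4.7%.

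**5. A second illustration, flow only.** It uses gamma stays with the Phase I means, scores discharged patients at −100%, and ties in-hospital change to remaining stay. Wilcoxon power falls from 91% to 53% (shape 2), 65% to 27% (shape 1) and 98% to 71% (shape 3). For shape 2 the mean difference shrinks from −28 to −18 points.

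**6. Does the repeated measures analysis cure it?** No. It has no discharge rule either. Where the SAP names software for such models it is PROC GLM with REPEATED, which drops any patient with a missing day.

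**The case against.** **Later tests are blocked.** A reader might infer that a wrongly failed oxygen step blocks the tests of respiratory failure, ICU admission and mortality that follow it. The documents give this little weight. The sequence opens with AE/SAE incidence, then NEWS2, then length of stay. Protocol 2.3 describes Phase I adverse events as the same in both groups. If the rates are truly equal, the first step succeeds in at most about 4.7% of trials, so the chain would usually stop before oxygen. SAP 9.6 also says secondary efficacy analyses get no multiplicity adjustment.

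**Faster discharge is tested directly.** Length of stay is its own endpoint (SAP 4.3), so a benefit that is only faster discharge is not lost to the trial. This stands. The damage is confined to the oxygen comparison.

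**The size is soft.** This also stands. The Phase I means are preliminary, come from 27 subjects, and compare Ampion with standard of care. Unequal loss between arms is an inference that depends on a drug effect; it is not a documented fact. At weak correlation the loss is modest.

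**Post-discharge contact.** SAP 8.1 contemplates telephone contact with discharged patients for ordinal status. That does not supply SpO2 or flow, which no section collects after discharge.

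**Copying the NEWS2 wording is not enough.** Correct. Severe disease can qualify on room air (Protocol 4.4), so baseline flow can be 0, and the percent change in SAP 5.6 divides by baseline. Deaths before Day 5 have no discharge value. For cytokines, Protocol 5.1.3 schedules Day 5 and Protocol 5.1.4 lists the discharge sample from Day 6 onward, so it is unclear whether an early leaver has a post-treatment sample.

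**Conclusion.** The gap stands on the text. SAP 4.4 requires a Day 5 value that is not collected after discharge, early discharge is foreseen, and the SAP's own NEWS2 rule was not applied to oxygen. Neither the missing-data rules nor the competing repeated measures analysis repairs it.

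The consequence is dilution and lost power if Ampion speeds recovery. It is not a false-positive risk. The illustrative loss runs from small (80% to 73%) to large (80% to 36%, or 91% to 53% under the flow model). It depends on the assumed stay distribution and on the assumed link between discharge and improvement, neither of which the documents give. The point concerns one mid-sequence secondary endpoint and should be corrected; it does not threaten the primary analysis. The cytokine mismatch is exploratory and minor.

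**What to change.** 1. In SAP 4.4, test the change at Day 5, or at discharge if earlier, using the last in-hospital SpO2, oxygen mode and flow (flow 0 on room air).
2. For flow, use absolute change, or ranks of it, because percent change is undefined at a baseline of 0.
3. Make the Wilcoxon test the named analysis and give deaths before Day 5 the worst rank.
4. Reconcile SAP 4.4 with the repeated measures analysis in the general text of SAP section 4 and in Protocol 9.4.2, so that one method is designated.
5. In SAP 4.8, use the sample after the last treatment, or at discharge, where one was taken before Day 5. State whether early leavers are expected to have one.

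Make the change before any unblinding. SAP 7.1 applies the interim analysis to secondary endpoint data, so that means before the interim.

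**Cost.** A few sentences in the SAP and an aligning edit in Protocol 9.4.2. The oxygen values are already recorded daily in hospital. The downside is that an early leaver's value is up to about four days earlier than Day 5.
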